Contingency management involved offering rewards contingent initially on attendance and then on negative urinalysis results for cannabis. Following assignment to the contingency management group, participants were introduced to the voucher programme at an initial information and assessment session. Participants were informed that they needed to achieve two weeks of abstinence to return a cannabis free urine. In week 1 of the intervention, participants received a £5.00 voucher for attending and providing a urine specimen independent of the drug test results with the aim of familiarising participants with the urine testing and voucher procedures. From week 2 until week 12 participants earned vouchers contingent upon consecutive negative specimens or specimens that indicated a reduction in cannabis use.

If the participant has a pre-planned holiday or other significant commitment, they were able, on a maximum of two occasions, to suspend the intervention for one week, returning after 2 weeks rather than after 1 week. They were still be expected to show evidence of abstinence

at that point, and they needed to request this suspension no later than at the time of their previous scheduled appointment. The Early Intervention team was also be able to request suspension of the intervention for a maximum of one month if a participant relapsed and lost capacity to decide whether they wished to continue. If capacity was not regained in one month, the intervention was not continued.

Optimised treatment as usual (to be delivered to the intervention and control groups)

Optimised treatment as usual for cannabis was a phase specific, individually tailored, psycho-educational approach to problematic cannabis use for generic early intervention care coordinators that applies general psycho-educational approaches used in first episode psychosis⁴. The full delivery was typically achieved over approximately three hours, normally offered over regularly programmed sessions of 15-30 minutes duration.

Sample size

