Assuming that 50% of the subjects in the control arm will not relapse during follow up,^{5 6} a 15% increase in this percentage due to intervention is clinically beneficial, and using a power of 90% and a significance level of 5%, a total sample size of 460 subjects will be required. This sample size is based on an analysis of time to relapse and will allow us to detect a 37% decrease in the hazard of relapse (hazard ratio of 0.63) in the intervention group using a Cox proportional hazards model. This sample size has been calculated using the Stata version 11⁷. The sample size is inflated by a factor of 1.06; assuming that the 120 care coordinators see an average of 4 service user participants in the trial and an intraclass correlation coefficient of 0.02, this gives a total sample size of 488. Finally, the sample size is inflated by 10% to account for drop outs (the primary outcome is obtainable from routine data), giving a total sample size of 544.

Randomisation

Participants were individually block randomised using blocks of size 2, 4 and 6 to either contingency management or optimised treatment as usual, stratified by severity of cannabis use (one to three times a week versus four or more times a week). Randomisation was carried out remotely and with impartiality by Sealed Envelope⁸.

Blinding

This was a single blind trial. Participants could not be blinded to their allocation as they will be participating in an interactive intervention. Outcome assessors were be blinded to allocation. However, this relied on participants, their care coordinators and clinical team not telling the assessors the.

The statisticians and health economists will remain blind to allocation until the primary analyses have been verified.

Outcomes

Primary Outcome

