The CONSORT¹⁻³ flow diagram will be constructed by/in collaboration with the Trial Manager who will have logs of service users who do and do not agree to take part in the study. It will include number of service users randomised to each arm of the trial, and the numbers who have follow up data available.

All analyses will be on an intention to treat basis and data from the pilot trial will be incorporated into the main trial.

Data will be analysed using Stata version 14¹⁵.

Descriptive statistics

Initial analyses will look at summary statistics for all variables, both overall and by randomised group. Summary statistics for continuous variables will be mean, median, SD, lower quartile, upper quartile, minimum and maximum and reported appropriately according to distribution. Summary statistics for categorical variables will be frequency and percentage within each category.

Summary statistics of baseline variables by whether a participant has dropped out of the study will also be examined to determine whether the drop outs had similar characteristics to those who remained in the study at baseline.

Analysis of the primary outcome

The primary outcome will be initially examined using Kaplan Meier survival curves by randomised allocation. If the assumptions of proportional hazards is satisfied, Cox Proportional Hazards modelling to compare the intervention and control groups will be carried out, adjusting for severity of cannabis use at baseline (the stratification variable, dichotomous – 1 to 3 times a week versus 4+ times a week) and whether the participant was part of the pilot trial. If the assumption of proportional hazards is not fulfilled, alternative modelling strategies will be employed. Robust standard errors will be used to account for clustering by therapist; which should account for most of the centre effects in this multicentre individually randomised trial. Hazard ratios and 95% confidence intervals will be presented.

Analysis of the secondary outcomes

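### The primary Cox analysis depends on an undefined proportional-hazards check with an open fallback, so a failed check leaves no pre-specified primary model or effect measure

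*SAP*

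**What the plan says.** In the SAP, *Analysis of the primary outcome* sets an order of steps. Kaplan-Meier curves by allocation come first. A Cox model adjusted for the cannabis-use stratifier and pilot status follows if proportional hazards holds. For the other case there is one sentence: "If the assumption of proportional hazards is not fulfilled, alternative modelling strategies will be employed". The section then specifies robust standard errors clustered by therapist and the reporting of hazard ratios with 95% confidence intervals. It gives no test, plot or threshold for the check, and no alternative model or order of preference. None of the six analyses under *Supportive analyses* deals with non-proportional hazards.

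Three other sections bear on this:

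- *Randomised treatments*: "From week 2 until week 12 participants earned vouchers contingent upon consecutive negative specimens or specimens that indicated a reduction in cannabis use".
- *Sample size*: the trial is sized to "detect a 37% decrease in the hazard of relapse (hazard ratio of 0.63) in the intervention group using a Cox proportional hazards model", that is, one constant ratio.
- *Blinding*: the statisticians stay blind to allocation until the primary analyses have been verified.

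**The concern.** Naming the primary estimator is the SAP's own task, and here it is named on one branch only. The other branch can be foreseen from the design: the active component stops at week 12, but relapses count for 18 months. If the effect fades, hazards are not proportional, and the model and effect measure would be settled after two curves have been seen.

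The pre-test is not needed to protect the type I error. If the two relapse curves are the same, the hazard ratio is 1 throughout and hazards are proportional by definition, so any failed check is a false alarm. The log-rank/Cox test is valid in that situation without a pre-test. What harms error control is freedom of choice after a failed check. What is at stake is mainly whether the trial has a defined primary estimate, and to a smaller degree the false-positive rate.

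**Working it through.** **1. The plan's own figure.** Inputs from *Sample size*: "Assuming that 50% of the subjects in the control arm will not relapse during follow up"; "a 15% increase in this percentage due to intervention is clinically beneficial"; "using a power of 90% and a significance level of 5%, a total sample size of 460 subjects will be required". Two-sided 5% and 1:1 allocation are assumed, as neither is stated.

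- Implied hazard ratio: ln 0.65 / ln 0.50 = 0.621 (SAP: 0.63).
- Events (Schoenfeld): 4 × (1.960 + 1.282)² / (ln 0.63)² = 42.03 / 0.2135 = 196.9, so 197.
- Mean event probability: (0.50 + 0.35) / 2 = 0.425. N = 197 / 0.425 = 464, against 460 stated.
- Design effect: 1 + (4 − 1) × 0.02 = 1.06; 460 × 1.06 = 487.6, so 488. Dropout: 488 / 0.9 = 542.2, so 543, against 544 stated.

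The sample size reproduces to within rounding and is not at fault. It was built on a Cox analysis with a constant ratio.

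**2. How much information comes after the vouchers stop.** Assume a constant control hazard with 50% relapse-free at 18 months (78 weeks). The share of control relapses falling by week 12 is (1 − 0.5^(12/78)) / 0.5 = 0.101 / 0.5 = 20%. About 80% fall later.

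**3. Type I error of the two-stage rule.** This is a simulation under assumptions that are not in the SAP: N = 488, exponential control hazard, 50% relapse, a check on Schoenfeld-type residuals at 5%, no clustering or covariates. The four analyses are Cox, restricted mean relapse-free time to 18 months, the hazard ratio to month 6, and the hazard ratio after month 6.

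| Rule under no effect | Type I error |
|---|---|
| Cox always | about 5.1% |
| Check, then one fixed restricted-mean fallback | about 5.5% |
| Check, then best of the four | about 7.4% |

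The check fails in about 5% of null trials, and about 50% of those then give at least one significant result. The last row follows: 0.95 × 5.1% + 0.05 × 50% = 4.8% + 2.5%, which is about 7.4% allowing for rounding. A separate simulation at N = 460 with other sets of fallbacks gave 6.6% (best of four) and 7.4% (best of six), with 34% and 51% significant among null trials sent to the fallback.

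**4. Behaviour when the effect wanes.** Same set-up, hazard ratio 0.5 and then 0.9:

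| Change point | Check fails | Cox power | Restricted-mean power |
|---|---|---|---|
| Week 12 | about 17% | about 32% | about 41% |
| Month 6 | about 39% | about 61% | about 77% |
| None (constant 0.63) | about 5% | about 92% | about 86% |

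The week-12 row matches the end of the vouchers. The month-6 row supposes a carry-over that the SAP does not describe. In either row the check passes in most trials although hazards are truly non-proportional, so it is a weak gate.

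**The case against.** A reader might infer that non-proportional hazards are likely, and that the trial therefore probably has no pre-specified primary estimate. The SAP does not support that. It says nothing about how the effect changes over time, and an effect that persists after week 12 is compatible with proportional hazards. Even under the waning patterns above, the check passes in about 61% to 83% of trials and the named Cox model would be used.

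A reader might also infer that error control is lost. It is not: the overall rise is from about 5% to at most about 7.4%. Reaching that figure requires trying four analyses and reporting whichever is significant. One fallback fixed in advance would cost about half a point.

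It can further be said that the fallback is not wholly free, because the sentences on clustered errors and hazard ratios come after it and may be meant to cover it. That is a fair reading, but it does not fix the estimate. A piecewise ratio, a time-varying ratio and a weighted ratio are all hazard ratios, and nothing says which one, over which period, would be primary.

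Blinding of the statisticians is a real safeguard. It limits choosing a method because it favours the intervention. It does not prevent choosing one for two-sided significance after seeing two unlabelled curves separate or cross.

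Finally, *Sample size* states its target first as a gain in the relapse-free percentage, so a restricted-mean primary analysis could also be defended. That stands. The essential request is that one analysis be named in advance; preferring Cox is a judgement.

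**Conclusion.** The point holds. The SAP makes its primary model conditional on a check that it does not define and leaves the alternative open. If the check fails, neither the primary model nor the effect measure is pre-specified. The open branch is plausible and foreseeable from the 12-week intervention and 18-month follow-up, but not shown to be likely.

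The effect on overall type I error is modest, about 0.4 points with one fixed fallback and about 2.3 points at the worst-case choice among four. Among null trials that reach the open fallback, it is about 50%. These figures rest on an exponential control hazard, 50% control relapse, the assumed hazard-ratio patterns, and no clustering or covariates. The textual gap does not depend on them. This should be corrected, but it does not undermine the design or the sample size.

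**What to change.** In *Analysis of the primary outcome*:

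1. State that the adjusted Cox hazard ratio with therapist-clustered standard errors is the primary analysis whatever the proportional-hazards check shows, and that it is read as an average hazard ratio over 18 months if hazards are not proportional.
2. Pre-specify one companion estimate, reported in all cases: the difference in restricted mean relapse-free time to 18 months, adjusted for the stratifier and pilot status.
3. Say how proportional hazards will be assessed, and use the result only to guide interpretation. Delete the open fallback.

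The cost is two or three sentences and one extra estimate. There is also a trade in power. When the effect is mainly early, Cox has less power than the restricted mean (about 61% against 77% with a month-6 change, 32% against 41% with a week-12 change). When hazards are proportional, as the sample size assumes, it has more (about 92% against 86%). A team that expects waning could make the restricted mean primary instead, provided that it says so before any curves by arm are seen.

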Social functioning, based on self-reports regarding engagement in work or study, defined as any work (including sheltered or voluntary) or study (full or part time). [outcome type: dichotomous]

Number of days cannabis is used in the previous 12 weeks for follow up at 12 weeks and previous six months for 18 month follow up [outcome type: count]

Number of admissions over 18 months follow up. The primary analysis of this outcome will be operationalised to include those who provided a full 18 months follow up and those who died during follow up [outcome type: dependent on number of events. It may be possible to use this as count data else it will be dichotomised to none versus any]

Data collection

Data were collected at three time points, baseline, 12 weeks and 18 months post baseline.

Baseline

Demographic and social information (age, gender, ethnicity, social standing, living arrangements, employment, benefits received)

Clinical characteristics

Cannabis use using Time Line Follow Back¹⁰

Part E of the Structured Clinical Interview for DSM IV¹¹

Urine sample results

The Positive and Negative syndrome scales (PANSS)⁹

Employment status using questions from the Client Service Receipt Inventory (CSRI)

SF-12 (to be used in health economic analysis)^{13, 14}

EQ-5D (to be used in health economic analysis)

CSRI tailored to the study¹³ (primarily for health economic analysis)

12 weeks and 18 months

Urine sample results

Positive and Negative Syndrome Scale (PANSS)⁹
Engagement in work or study from the CSRI
SF-12 (to be used in health economic analysis)^{13,14}
EQ-5D (to be used in health economic analysis)
CSRI (to be used in health economic analysis)

18 months

Date of admission to hospital or crisis resolution team

Data entry

Data were entered using a web based system set up by Sealed Envelope⁸. This was set up so that, it mirrored the data collection sheets in order. It also had range checks, consistency checks and for closed questions gave a number of options plus “other” where appropriate. Assessors who entered the data will had no access to the group allocation through this system.

Data were checked by the statistician and health economists before analysis and any problems reported to the Trial Manager, who will rectify them as appropriate before data analysis.

Statistical analyses

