These will be analysed separately for data collected at 12 weeks and 18 months. Models will include severity of cannabis use at baseline and whether the participant was part of the pilot trial. For the dichotomous outcomes (cannabis positive urine, engaged in work or study), logistic regression with robust standard errors to account for clustering by therapist will be used. If there are too few participants engaged in work or study for logistic regression to be possible then results will be reported descriptively. For continuous outcomes (positive and negative symptoms), linear regression with robust standard errors will be used.

For count outcomes, Poisson regression with robust standard errors will be used for count outcomes (number of cannabis days and number of admissions over follow up). If there are excess zeros for either count outcome, then the use of zero inflated Poisson regression will be explored.

Appropriate estimates and 95% confidence intervals will be presented for all analyses.

Missing data

There is not much missing data for the primary outcome since it is an objective outcome collected from the appropriate informatics departments.

There is missing data for other variables, especially at follow up. This may be because of non-attendance at the follow up appointment or non-response to specific questions. The extent and patterns of missingness will be assessed. Potential predictors of missing values that are related to the outcomes will be identified. .

Multiple imputation¹⁶ may be used if it is felt to be necessary. We will only impute outcome data if surrogate outcomes or variables closely related to the missing outcome(s) are available. Otherwise there is no gain in imputing outcomes¹⁷.

The primary analysis will be complete case analysis with analysis using multiple imputation being a supportive analysis if it is carried out.

Supportive analyses

There will be up to six supportive analyses for the primary outcome:

1. Analysis of all outcomes with their baseline predictors of missingness, that is modelling including the randomised allocation, whether the participant was in the pilot trial and the level of cannabis use at baseline

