2. Analysis of the primary outcome excluding those participants who have no follow up secondary outcome data (for 12 weeks and 18 months separately) because those who drop out or die may be different to those who remain in the study and/ or survive. Before doing this, some demographic statistics comparing those who remained in the study and those who dropped out will be produced.
3. Analysis of those in the main trial only as some changes were made to the protocol at the end of the pilot before the main trial commenced, which might mean the participants behave differently to those in the pilot trial.
4. Analysis of the primary outcome controlling for the same factors as in the primary analysis plus the number of psychoeducation sessions attended (which is being offered in both arms of the trial).
5. Analysis of the primary outcome controlling for the same factors as the primary analysis and number of admissions in the six months prior to baseline.

6. Analysis of the primary outcome controlling for the same factors as the primary analysis, but using centre as the clustering variable not therapist.

There will be up to two supportive analyses for the number of admissions during follow up:

1. In addition to the factors included in the main analysis, this will include predictors of missingness.

2. Including those who were discharged within 18 months and assuming they had no admissions over the follow up time.

There may be supportive analyses for secondary outcomes collected at 18 months, as outlined in the missing data section.

Exploratory analysis:

We will investigate potential patterns and degree of non-compliance using clinical definitions of compliance and descriptive analysis. We will perform a Complier Average Causal Effect (CACE) analysis if feasible.

There are no subgroup analyses planned.

Health Economic analyses

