The objective of the cost effectiveness analysis is to establish the relative cost-effectiveness of contingency management versus optimised treatment as usual at 18 months. The primary outcome will be QALYs (Quality Adjusted Life Years) calculated using EuroQol EQ-5D (3L) health profiles combined with health state preference values from the UK general populationⁱ. The resultant mean Quality of Life utility scores of the two treatment groups will be compared at eighteen months using unpaired *t*-tests. QALYs will be calculated using the area under the curve method and compared between groups adjusting for baseline EQ-5D utility scoresⁱⁱ.

Costs will be calculated based on resource use gathered from an adapted version of the client services receipt inventory (CSRI)ⁱⁱⁱ. The primary analysis will take an NHS and personal social services perspective^{iv}.

Costs of the contingency management intervention and optimised treatment as usual will be calculated using the salaries of staff delivering the intervention, plus employer on-costs, overhead costs, the cost of providers of supervision, and the cost of any equipment or consumables. A ratio of direct face-to-face to indirect non-face-to-face time will be applied.

Total costs at 18 months will be calculated by combining resource use with unit costs at 2016 prices. Unit costs will be derived from PSSRU and NHS reference costs. Medications will be costed using NHS prescription cost analysis data. Costs and QALYs will be discounted at 3.5% per year.

Costs will be compared, adjusting for baseline differences. Patient level costs and quality of life data will be bootstrapped with replacement (N = 10,000) to populate incremental cost effectiveness (ICER) planes, to estimate median cost-effectiveness and (pseudo) 95% confidence intervals. The probability of the intervention being cost-effective at different levels of willingness to pay for health benefits will be shown by generating cost-effectiveness acceptability curves (CEACs).

No subgroup health economics analyses are planned. The CHEERS statement will be completed^v.

Additional health economics analyses

1. Cost effectiveness at 3 months will be reported.
2. Results from a broader perspective including costs from criminal justice and cost of unpaid lost productivity due to illness will be reported.
3. Cost-effectiveness using alternative outcomes will be reported:
 - QALYs calculated using SF-12 data
 - Time to relapse (to 18 months)

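### The secondary outcome models and the 18-month utility comparison leave out baseline values that the trial collected, which costs precision and protection against chance imbalance

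*SAP*

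**What the plan says.** SAP, Analysis of the secondary outcomes, gives one covariate list for all models at 12 weeks and 18 months: "Models will include severity of cannabis use at baseline and whether the participant was part of the pilot trial". Analysis of the primary outcome defines severity as "the stratification variable, dichotomous – 1 to 3 times a week versus 4+ times a week", and I read the secondary models as using the same variable.

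The model types follow without any further covariate. PANSS: "For continuous outcomes (positive and negative symptoms), linear regression with robust standard errors will be used". Urine and work/study: "For the dichotomous outcomes (cannabis positive urine, engaged in work or study), logistic regression with robust standard errors to account for clustering by therapist will" (the sentence adds no covariate after this). Cannabis days and number of admissions go to Poisson regression.

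The baseline list under Data collection includes "Cannabis use using Time Line Follow Back" and, further down, "The Positive and Negative syndrome scales (PANSS"), as well as urine results, employment questions from the CSRI, and EQ-5D. Earlier admissions are not on that list. They appear only in Supportive analyses, item 5, which adjusts the primary outcome for "number of admissions in the six months prior to baseline".

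Health Economic analyses sets a t-test without covariates for utility: "Quality of Life utility scores of the two treatment groups will be compared at eighteen months using unpaired". The next sentence adjusts QALYs for baseline EQ-5D utility, and costs are later adjusted for baseline differences.

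**The concern.** The baseline value of a repeated measure is usually its strongest single predictor. A two-level cannabis frequency variable is unlikely to say much about PANSS, work or utility. Randomisation was stratified on cannabis frequency alone, so these other variables are balanced only by chance, and the planned models cannot correct an imbalance that happens to occur.

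Reduced cannabis use, fewer positive symptoms and more work or education are among the trial's stated aims, so wider intervals here matter. Complete-case analysis is also the main approach and the SAP expects missing follow-up data. Conditioning on the baseline value would let follow-up depend on that value, a weaker assumption than the planned models need. The SAP gives nothing from which to size this last benefit.

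The utility t-test also departs from the method that the SAP itself uses for QALYs in the same paragraph.

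**Working it through.** **The plan's own figures.** The SAP states no power or precision for any secondary outcome or for utility. Its only sample size is for time to relapse, and it reproduces closely. At a hazard ratio of 0.63, 90% power and two-sided 5% (sidedness assumed), Schoenfeld's formula gives 197 events. With a mean event proportion of (0.50 + 0.35)/2 = 0.425 that is 197/0.425 = 464, against 460 stated. Then 460 × (1 + 3 × 0.02) = 487.6, i.e. 488, and 488/0.90 = 542.2, i.e. 543, against 544 stated. I use 544 (272 per arm) below.

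**Is the gap filled elsewhere?** No supportive analysis is defined as adding an outcome's own baseline value. Item 1 concerns baseline predictors of missingness and, as spelled out, names only allocation, pilot status and baseline cannabis level. The supportive analyses of admissions add predictors of missingness and a different rule for people discharged early.

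**Precision, continuous outcomes.** Let *r* be the correlation between baseline and follow-up that remains after the two planned covariates. The SAP does not give it, so it is an assumption. Adding the baseline value multiplies residual variance by 1 − *r*², interval width by √(1 − *r*²), and effective sample size by 1/(1 − *r*²). Clustering is ignored. For power, take an effect that the unadjusted comparison detects with 80% power, (1.96 + 0.84) × √(2/272) = 0.24 SD. Adjusted power is then Φ(2.80/√(1 − *r*²) − 1.96).

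| *r* | Variance factor | Interval width factor | Equivalent sample factor | Power (80% unadjusted) |
|---|---|---|---|---|
| 0.3 | 0.91 | 0.95 | 1.10 | 83.6% |
| 0.5 | 0.75 | 0.87 | 1.33 | 89.9% |
| 0.6 | 0.64 | 0.80 | 1.56 | 93.8% |

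A simulation of 2,000 trials at 544 participants and *r* = 0.5 agrees: 81% power unadjusted, 90% adjusted. The power column is unchanged at smaller numbers if the effect is rescaled to 80% unadjusted power.

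**Chance imbalance.** The standard error of a baseline difference is √(2/272) = 0.086 SD. An imbalance of 1.96 standard errors (0.168 SD) shifts the unadjusted effect by *r* × 0.168: 0.05 SD at *r* = 0.3 and 0.08 SD at 0.5. Given that imbalance, the test statistic has mean 1.96*r* and standard deviation √(1 − *r*²), so the two-sided type I error rises from 5% to about 8% and 13%. Averaged over all randomisations it remains 5%.

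**Binary outcomes.** The factors above do not carry over. In a simulation with an assumed 70% baseline prevalence and a baseline odds ratio of 6, neither from the SAP, power went from 75% to 81%. The odds ratio then becomes conditional on the added covariate, and its standard error need not shrink.

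**The case against.** The strongest reply is that the planned analysis is valid. A stratifier-adjusted comparison of randomised groups is unbiased, and its interval already allows for chance imbalance. A reader might infer that the secondary results would be biased. The documents do not support that: the loss is of efficiency and of protection in the particular sample drawn.

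A reader might also infer that no outcome has any of its own baseline in its model. That goes too far. For cannabis days, and in part for urine, the stratifier is a coarsened baseline, so only the loss from dichotomising remains.

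Other limits also stand:

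- **Urine.** Entry requires regular use over the previous six months, so baseline urine is probably positive in nearly everyone. It would add little and could produce sparse cells.
- **Work/study.** The SAP already foresees too few events for logistic regression. The baseline list names employment; baseline study status is inferred from the CSRI.
- **Admissions.** The prior count is not in the baseline list, and for the closely related primary outcome the authors placed it in a supportive analysis.
- **Utility.** The t-test does not feed the cost-effectiveness ratio or the acceptability curves, since QALYs and costs are adjusted. Its neglect of clustering is minor: with the planned design effect of 1.06, standard errors change by about 3% (√1.06 = 1.03).

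These points narrow the concern. They do not answer it for PANSS, for work/study where numbers allow, or for the utility comparison.

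**Conclusion.** The point holds as a matter of efficiency. The secondary models adjust only for the dichotomous stratifier and pilot status, and the 18-month utility comparison adjusts for nothing, although usable baseline measures exist. For PANSS and utility the cost is 9% to 36% of residual variance, or intervals about 5% to 20% wider than they could be narrowed to, over an assumed *r* of 0.3 to 0.6. The true size depends on a correlation that the SAP does not report. The gain is smaller for cannabis days. For work/study it would be a gain in power, and it depends on event numbers.

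The primary outcome, the QALY comparison and the cost comparison are untouched, and no stated figure is wrong. The utility t-test is inconsistent with the SAP's own treatment of QALYs, but a reader should not infer that the cost-effectiveness conclusion rests on it.

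**What to change.** Before unblinding, amend the main models as follows:

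- **PANSS:** add the baseline positive or negative score to the corresponding linear model.
- **Work/study:** add baseline status, as available from the CSRI, where event numbers allow, and state that the odds ratio is then conditional on it.
- **Cannabis days:** add baseline Time Line Follow Back days, with the functional form named in advance.
- **18-month utility:** replace the t-test by linear regression on arm, baseline EQ-5D utility, the stratifier and pilot status, with therapist-clustered standard errors.
- **Missing baseline values:** for EQ-5D, use the chained-equation imputation already specified under Additional health economics analyses, item 4. For the other covariates, use mean imputation or a missing indicator so that no participant is dropped.

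Adjustment for baseline urine result and for earlier admissions is optional.

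No new data are needed. The cost is SAP wording plus a dated justification, because follow-up was planned to run to September 2017 and the final SAP is dated 04/12/2017. The Blinding section keeps statisticians and health economists blind until the primary analyses are verified, so the change can still be made without knowledge of allocation if it is made before then.
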